8.8.2 Dose Modifications During the Ramp-up Phase

Dose should be interrupted or reduced for toxicities according to [Table 6](#) and [Table 9](#).

Ramp-up phase of venetoclax will be performed at regular scheduled visits. In cases when dose modification of venetoclax needs to be performed at an unscheduled visit (e.g., due to dosing interruption or reduction of venetoclax which leads to changed treatment schedule of venetoclax), relevant evaluations and safety measures should be performed (see Section 9.2.8).

In exceptional cases duly justified due to other reasons, during the safety run-in phase patients might discontinue venetoclax treatment permanently per discussion between the Investigator and sponsor's medical monitor to ensure patient safety.

8.8.3 Dose Modifications After the Ramp-up Phase

Dose should be interrupted or reduced for toxicities according to [Table 6](#) and [Table 9](#).

Note: Dose modifications below 100 mg daily dose are not allowed, once the individual highest dose of venetoclax is reached. Patients who need dose reductions below 100 mg daily dose should discontinue venetoclax treatment permanently and may proceed with MOR00208 treatment only, per discussion between the Investigator and sponsor's medical monitor.

8.8.4 Dose Modifications of Venetoclax for Use with CYP3A, P-gp, BCRP and OATP Inhibitors

Concomitant use of venetoclax with strong or moderate CYP3A inhibitors (e.g., strong: ketoconazole, conivaptan, clarithromycin, indinavir, itraconazole, lopinavir, ritonavir, telaprevir, posaconazole and voriconazole; moderate: erythromycin, ciprofloxacin, diltiazem, fluconazole, verapamil) or inducers (e.g., strong: carbamazepine, phenytoin, rifampin, St. John's wort; moderate: bosentan, efavirenz, etravirine, modafinil, nafcillin) during ramp-up phase is

contraindicated. Co-administration of CYP3A4 inducers may lead to decreased venetoclax exposure and consequently a risk for lack of efficacy. Concomitant use of venetoclax with strong CYP3A inhibitors increases venetoclax exposure (i.e., C_{max} and AUC) and may increase the risk for TLS during ramp-up phase. For patients who have completed the ramp-up phase and are on a steady daily dose of venetoclax, reduce the venetoclax dose by at least 50% when moderate CYP3A inhibitors and 75% when *strong* CYP3A inhibitors must be used concomitantly, but not below 100 mg. Patients should be monitored more closely for signs of toxicities and the dose may need to be further adjusted. The venetoclax dose that was used prior to initiating the CYP3A inhibitor should be resumed 2 to 3 days after discontinuation of the inhibitor.

Venetoclax is a P-gp, breast cancer resistance protein (BCRP) and organic anion-transporting polypeptide (OATP) inhibitor *in vitro*. Therefore, avoid concomitant use of venetoclax with P-gp and BCRP inhibitors and substrates (BCRP substrates: e.g., digoxin, dabigatran, everolimus, sirolimus; P-gp substrates: e.g., digoxin, everolimus, and sirolimus) and consider alternative treatments. If a statin (OATP substrate) is used concomitantly with venetoclax, close monitoring of statin-related toxicity is recommended. *In vitro* data suggest venetoclax has inhibition potential on P-gp substrates at therapeutic dose levels in the gut. Co-administration of a single dose of rifampin, a P-gp inhibitor, increased venetoclax C_{max} by 106% and AUC_{∞} by 78%. Therefore, if a narrow therapeutic index P-gp inhibitor must be used, then it should be taken at least 6 hours before venetoclax and reduce the venetoclax dose by at least 50%, but not below 100 mg after the ramp-up phase. Monitor these patients more closely for signs of toxicities. Resume the venetoclax dose that was used prior to initiating the P-gp inhibitor 2 to 3 days after discontinuation of the inhibitor.

The recommendations for managing drug-drug interactions are summarized in [Table 7](#).

Table 7: Management of Potential Venetoclax Interactions with CYP3A Inhibitors or Inducers, BCRP and P-gp Inhibitors and Substrates

Inhibitors	Ramp-Up Phase	Steady Daily Dose (After Ramp-Up Phase)
Strong and moderate CYP3A inhibitors and inducers	Contraindicated	Avoid inhibitor use or reduce venetoclax dose by at least 75% when strong and 50% when moderate CYP3A inhibitors, but not below 100 mg
P-gp and BCRP inhibitors and substrates	
P-gp and BCRP inhibitors, or narrow therapeutic index P-gp substrates; furthermore, grapefruit products, Seville oranges, and starfruit (carambola) should be avoided during treatment with venetoclax.
 
If a P-gp inhibitor must be used, reduce venetoclax dose by at least 50%, but not below 100 mg after the ramp-up phase.
 
If a narrow therapeutic index P-gp substrate must be used, it should be taken at least 6 hours before venetoclax.
	

MorphoSys AG Proprietary Information

8.9 Guidance for Managing Specific Adverse Events for the Combination of MOR00208 and Idelalisib

Recommendations for managing specific adverse events (based on the FDA Prescribing Information and the European SmPC) are summarized in Table 8.

Table 8: Guidance for Study Drug (Idelalisib/MOR00208) Dose Modifications Based on Type and Severity of Treatment-Emergent Adverse Events or Laboratory Abnormalities

NCI CTCAE Grade	Recommendation	
	Idelalisib	MOR00208
HEMATOLOGICAL ADVERSE EVENTS		
Neutropenia		
Grade 2 ($<1.5-1.0 \times 10^9/L$)	Maintain current dose level and schedule.	Maintain dosing as per protocol.
Grade 3 ($<1.0-0.5 \times 10^9/L$)	Maintain current idelalisib dose level and schedule. Monitor ANC at least weekly. Consider growth factor support.	Maintain dosing as per protocol. Monitor ANC at least weekly. Consider growth factor support.
Grade 4 ($<0.5 \times 10^9/L$) or occurrence of neutropenic fever or infection	Withhold idelalisib and monitor ANC at least weekly until ANC $\geq 0.5 \times 10^9/L$ and/or neutropenic fever or infection is resolved. Thereafter may resume idelalisib at lower (100 mg BID) dose at Investigator's discretion. Consider growth factor support.	Withhold MOR00208 and monitor ANC at least weekly until ANC $\geq 0.5 \times 10^9/L$ and/or neutropenic fever or infection is resolved. Thereafter, may resume as per protocol. Consider growth factor support.
Thrombocytopenia		
Grade 2 ($<75-50 \times 10^9/L$)	Maintain current dose level and schedule.	Maintain dosing as per protocol.
Grade 3 ($<50-25 \times 10^9/L$)	Maintain current dose level and schedule. Monitor platelets at least weekly.	Maintain dosing as per protocol. Monitor platelets at least weekly.
Grade 4 ($<25 \times 10^9/L$)	Withhold idelalisib until platelet count reach $\geq 25 \times 10^9/L$. Consider transfusion support. Monitor platelets at least weekly. May resume idelalisib at lower (100 mg BID) dose level when platelet counts have returned to $\geq 25 \times 10^9/L$.	Withhold MOR00208 until platelet count reach $\geq 25 \times 10^9/L$. Consider transfusion support. Monitor platelets at least weekly. Thereafter, may resume dosing as per protocol.
Anemia		
Grade ≥ 3 (Grade 3 defined as: Hemoglobin <8.0 g/dL; <4.9 mmol/L; <80 g/L; transfusion indicated)	Maintain dosing as per protocol. Consider transfusion and growth factor support in accordance with institutional guidelines.	Maintain dosing as per protocol. Consider transfusion and growth factor support in accordance with institutional guidelines.
Grade 4 (Life-threatening consequences; urgent intervention indicated)	Withhold idelalisib until Grade 3 and monitor at least weekly. Thereafter, maintain dosing as per protocol.	Withhold MOR00208 until Grade 3 and monitor at least weekly. Thereafter, maintain dosing as per protocol.

NCI CTCAE Grade	Recommendation	
	Idelalisib	MOR00208
NON-HEMATOLOGICAL ADVERSE EVENTS		
Dermatological Events		
Grade ≤2	Maintain current dose and schedule. Monitor patients for the development of severe cutaneous reactions.	Maintain dosing as per protocol. Monitor patients for the development of severe cutaneous reactions.
Grade 3 or 4	Withhold idelalisib until Grade ≤1 is reached. May resume at lower dose (100 mg BID) at Investigator's discretion. Discontinue idelalisib permanently if rechallenge results in recurrence of Grade 3-4 toxicity.	Withhold MOR00208 until Grade ≤2 is reached and thereafter may resume dosing as per protocol.
CAVE: Stevens-Johnson syndrome/ Toxic epidermal necrolysis	If Stevens-Johnson syndrome or toxic epidermal necrolysis is suspected, treatment with idelalisib should be immediately and permanently discontinued and the patient treated accordingly.	If Stevens-Johnson syndrome or toxic epidermal necrolysis is suspected, treatment with MOR00208 should be immediately and permanently discontinued and the patient treated accordingly.
Gastrointestinal Events (Diarrhea/Colitis)		
All Grades	Obtain patient history, perform physical examination and diagnostic work-up to rule out infectious etiology. Provide adequate symptomatic support including oral hydration/i.v. fluid supplementation, dietary modification and antimotility agents as warranted. Supportive care should be provided until diarrhea Grade ≤1. If the infection can be ruled-out follow below mentioned diarrhea-management recommendations. For patients who develop severe abdominal pain, particularly if early during therapy, the possibility of a bowel obstruction or perforation should be considered. Appropriate clinical and radiographic examination should be performed, and supportive care and surgical intervention should be considered. Idelalisib treatment should be discontinued permanently in patients who experience intestinal perforation (see details in Section 8.9.2).	
Grade 2 (increase of 4-6 stools per day over baseline – moderate diarrhea)	Maintain dosing as per protocol. Monitor at least weekly until resolved.	Maintain dosing as per protocol. Monitor at least weekly until resolved.
Grade 3 (increase of ≥ 7 stools per day over baseline, fecal incontinence – severe diarrhea)	Withhold idelalisib until Grade ≤1. Monitor at least weekly until resolved, then may resume at lower dose (100 mg BID).	Maintain dosing as per protocol. In case diarrhea/colitis does not respond to antimotility agents or patient's general condition deteriorates, withhold MOR00208 until Grade ≤2 is reached and thereafter may resume dosing as per protocol.
Grade 4 (life-threatening)	Discontinue idelalisib permanently.	Withhold MOR00208 until Grade ≤2 is reached and thereafter may resume dosing as per protocol.

NCI CTCAE Grade	Recommendation	
	Idelalisib	MOR00208
Hepatic Events (Elevations in ALT, AST, or bilirubin)		
Grade 2 (ALT/AST>3-5xULN) (Bilirubin>1.5-3xULN)	Maintain current dose level and schedule. Monitor ALT, AST and bilirubin at least weekly.	Maintain dosing as per protocol. Monitor ALT, AST and bilirubin at least weekly.
Grade 3 (ALT/AST>5-20xULN) (Bilirubin>3-10xULN)	Withhold idelalisib. Monitor for liver toxicity at least weekly until all abnormalities are Grade ≤1 or to baseline values. Then may resume at lower dose (100 mg BID).	Withhold MOR00208. Monitor for liver toxicity at least weekly until all abnormalities are Grade ≤1 or to baseline values. Thereafter, may resume dosing as per protocol.
Grade 4 (ALT/AST>20xULN) (Bilirubin>10xULN)	Discontinue idelalisib permanently.	Withhold MOR00208. Monitor for liver toxicity at least weekly until all abnormalities are Grade ≤1 or to baseline values. Thereafter, may resume dosing as per protocol.
Pulmonary Events (Pneumonitis or Organizing pneumonia)		
Grade 1	Maintain current dose and schedule if patient is asymptomatic. CAVE: If pneumonitis or organizing pneumonia is suspected with any severity of symptoms, interrupt idelalisib treatment until the etiology of the pulmonary symptoms has been determined. Patients with pneumonitis or organizing pneumonia thought to be caused by idelalisib should be treated with discontinuation of idelalisib and administration of corticosteroids. Monitor patient until resolved.	Maintain dosing as per protocol. Monitor patient until resolved or symptoms subside.
Grade 2	Discontinue idelalisib permanently.	Maintain dosing as per protocol. Monitor patient until resolved.
Grade ≥3	Discontinue idelalisib permanently.	Withhold MOR00208 until toxicity diminishes in severity to Grade ≤2. Thereafter, may resume dosing as per protocol.
Serious infections		
Pneumocystis jirovecii pneumonia (PJP)		
Prophylaxis for PJP during and after idelalisib treatment	Prophylaxis for PJP should be administered to all patients throughout idelalisib treatment, and for a period of 2 to 6 months after discontinuation. The duration of post-treatment prophylaxis should be based on clinical judgment and may take into account a patient's risk factors such as concomitant corticosteroid treatment and prolonged neutropenia.	
Any Grade	Idelalisib treatment should be interrupted in patients with suspected PJP infection of any grade and permanently discontinued if PJP infection is confirmed. Appropriate	MOR00208 administration should be withheld for patients with suspected PJP infection of any grade and permanently discontinued if PJP infection is confirmed. Appropriate

NCI CTCAE Grade	Recommendation	
	Idelalisib	MOR00208
	medical therapy or other interventions should be instituted.	medical therapy or other interventions should be instituted.
Cytomegalovirus (CMV)		
CMV monitoring	A central CMV laboratory test (serology and polymerase chain reaction [PCR]) will be performed for all patients at screening. Patient with negative serology should be monitored locally in accordance with institutional guidelines. Patient with positive serology or with other evidence of a history of CMV infection should be carefully monitored with a PCR based methodology: 
 monthly, if the initial PCR result was negative without associated clinical signs of CMV infection weekly, if significant CMV viremia is detected. 	
Any Grade	For patients with evidence of CMV viremia and clinical signs of CMV infection, idelalisib should be immediately interrupted until the infection has resolved per discussion between the Investigator and sponsor's medical monitor. If the benefits of resuming idelalisib are judged to outweigh the risks, consideration should be given to administering pre-emptive CMV therapy in accordance with institutional guidelines.	For patients with evidence of CMV viremia and clinical signs of CMV infection, MOR00208 should be immediately interrupted until the infection has resolved per discussion between the Investigator and sponsor's medical monitor. If the benefits of resuming MOR00208 are judged to outweigh the risks, consideration should be given to administering pre-emptive CMV therapy in accordance with institutional guidelines.

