Management: Patients enrolling in Cohort B will be assessed for TLS risk and should receive appropriate prophylaxis for TLS as described in detail in Section 8.5 and 9.3.3.6. Importantly, all patients in Cohort B, who participate in the safety run-in phase, will be hospitalized on the day of the first two dose escalations of venetoclax (C1D8 and C1D15). Nephrology or acute dialysis service should be consulted or contacted on admission per institutional standards to ensure emergency dialysis is available and the appropriate staff is aware and prepared to handle any necessary intervention for TLS.

MOR00208 should be withheld for any events of clinical TLS (clinical TLS is defined as laboratory TLS with clinical consequences such as acute renal failure, cardiac arrhythmias, or sudden death and/or seizures). After resolution MOR00208 therapy may be resumed at the discretion of the physician.

During the ramp-up phase with venetoclax blood chemistries should be monitored and abnormalities should be managed promptly. Dosing should be interrupted if needed. More intensive measures should be employed (intravenous hydration, frequent monitoring, hospitalization) as overall risk increases. For any events of clinical TLS, resume venetoclax at a reduced dose following resolution. Concomitant use of venetoclax with strong or moderate CYP3A inhibitors or inducers within 7 days prior to the first dose of venetoclax and during ramp-up phase of venetoclax is contraindicated. P-gp and BCRP inhibitors increases venetoclax exposure may increase the risk of TLS; therefore, concomitant use of venetoclax with P-gp and

BCRP inhibitors at initiation and during ramp-up phase should be avoided and requires venetoclax dose adjustment.

Patients should be advised of the potential risk of TLS to immediately report any signs and symptoms associated with this event (fever, chills, nausea, vomiting, confusion, shortness of breath, seizure, irregular heartbeat, dark or cloudy urine, unusual tiredness, muscle pain, and/or joint discomfort) to their doctor for evaluation, and to be adequately hydrated every day when taking venetoclax to reduce the risk of TLS.

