- CYP2C8 substrates: *In vitro*, idelalisib both inhibited and induced CYP2C8, but it is not known whether this translates to an *in vivo* effect on CYP2C8 substrates. Caution is advised if idelalisib is used together with narrow therapeutic index drugs that are substrates of CYP2C8 (e.g., paclitaxel).
- Substrates of inducible enzymes (e.g., CYP2C9, CYP2C19, CYP2B6 and UGT): *In vitro*, idelalisib was an inducer of several enzymes, and a risk for decreased exposure and thereby decreased efficacy of substrates of inducible enzymes such as CYP2C9, CYP2C19, CYP2B6 and UGT cannot be excluded. Caution is advised if idelalisib is used together with narrow therapeutic index drugs that are substrates of these enzymes (e.g., warfarin, phenytoin, S-mephenytoin).
- Breast cancer resistance protein (BCRP), organic anion-transporting polypeptide (OATP)1B1, OATP1B3 and P-gp substrates: Co-administration of multiple doses of idelalisib 150 mg twice daily to healthy subjects resulted in comparable exposures for

rosuvastatin (AUC 90% CI: 87, 121) and digoxin (AUC 90%; CI: 98, 111 [sic, SmPC]), suggesting no clinically relevant inhibition of BCRP, OATP1B1/1B3 or systemic P-gp by idelalisib. A risk for P-gp inhibition in the gastrointestinal tract, that could result in increased exposure of sensitive substrates for intestinal P-gp such as dabigatran etexilate, cannot be excluded.

Cohort B only: The following medications should be avoided:

Avoid concomitant use of venetoclax with strong or moderate CYP3A inhibitors or inducers after the ramp-up phase of venetoclax. P-gp and BCRP inhibitors, or narrow therapeutic index P-gp substrates; furthermore, grapefruit products, Seville oranges, and starfruit (carambola) should be avoided during treatment with venetoclax. Consider alternative treatments.

The recommendations for managing drug-drug interactions and dose modifications of venetoclax are summarized in [Table 7](#) and detailed in Section 8.8.4.

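### Protocol Section 8.8.4 merges two venetoclax interaction rules under the wrong drug class and so conflicts with Table 7

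*Protocol*

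**What the plan says.** Section 8.8.4 of the protocol covers venetoclax dosing alongside interacting drugs in Cohort B. Its paragraph on P-gp, BCRP and OATP first asks sites to avoid P-gp and BCRP inhibitors and substrates and to look for alternatives. For the unavoidable case it then says that "if a narrow therapeutic index P-gp inhibitor must be used, then it should be taken at least 6 hours before venetoclax". The same sentence ties a second action to that trigger: venetoclax is to be cut by half or more, with a floor of 100 mg once ramp-up is over. That is one trigger with two actions.

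Table 7, introduced as the summary of these recommendations, gives two triggers with one action each:

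- The dose rule, for inhibitors: "If a P-gp inhibitor must be used, reduce venetoclax dose by at least 50%, but not below 100 mg after the ramp-up phase"
- The timing rule, for substrates: "If a narrow therapeutic index P-gp substrate must be used, it should be taken at least 6 hours before venetoclax"

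Two other sections bear on the point. Section 8.13 lists what Cohort B patients should avoid as "P-gp and BCRP inhibitors, or narrow therapeutic index P-gp substrates", and then refers sites to Table 7 for the summary of interaction management, "and detailed in Section 8.8.4". Section 8.10.1, on tumor lysis syndrome, says that use with P-gp and "BCRP inhibitors at initiation and during ramp-up phase should be avoided and requires venetoclax dose adjustment".

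**The concern.** The running text and its own summary table disagree on which drugs trigger which action. In the text, the narrow therapeutic index qualifier is attached to inhibitors and governs both actions. In Table 7 it is attached to substrates and governs only the timing.

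This is an operative dosing-safety instruction. P-gp inhibitors raise venetoclax exposure, and Section 8.10.1 links that to tumor lysis risk. A site that acts on the sentence without checking the table could leave venetoclax unreduced when Table 7 would at least halve it. It would also find no advice on separating doses of a narrow-index substrate. Section 8.13 describes Section 8.8.4 as the detailed source, and no rule says which text prevails, so a site could reasonably treat the sentence as controlling.

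**Working it through.** No sample size, power or error rate is involved. The check sets the texts side by side and then applies the dose rule.

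**Step 1. Compare the two rules.**

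| Situation after ramp-up | Section 8.8.4 sentence, read alone | Table 7 |
|---|---|---|
| P-gp inhibitor, narrow-index | 6-hour separation and reduction of at least 50% | Reduction of at least 50% |
| P-gp inhibitor, not narrow-index | No instruction | Reduction of at least 50% |
| Narrow-index P-gp substrate | No instruction | 6-hour separation, no reduction |

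The two sources do not fully agree in any row.

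**Step 2. Decide which text is wrong.**

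- Section 8.8.4 gives two different reasons. Venetoclax may inhibit P-gp in the gut, which affects substrates and supports separating the doses. For the other direction it reports: "Co-administration of a single dose of rifampin, a P-gp inhibitor, increased venetoclax" Cmax by 106% and AUC by 78%. That supports reducing venetoclax with an inhibitor, and it carries no narrow-index qualifier. Two reasons acting in opposite directions call for two rules, as in Table 7.
- The resumption rule that closes the paragraph speaks of the P-gp inhibitor without the qualifier.
- Section 8.13 attaches narrow therapeutic index to substrates, as Table 7 does.
- Section 8.10.1 calls for dose adjustment with P-gp and BCRP inhibitors and sets no narrow-index limit. It covers only initiation and ramp-up, so it supports the drug class but not the post-ramp-up rule, which rests on Table 7.

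All four point to the sentence as the error.

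**Step 3. Work out the dose difference.** Under Table 7, after ramp-up with a P-gp inhibitor:

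maximum venetoclax dose = max(100 mg, 0.5 × current dose)

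- From 400 mg: max(100, 200) = 200 mg
- From 200 mg: max(100, 100) = 100 mg
- From 100 mg: max(100, 50) = 100 mg, the floor

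Under the sentence read alone, with an inhibitor that is not narrow-index, there is no reduction: 400 mg stays 400 mg and 200 mg stays 200 mg. The dose is then at least twice what Table 7 allows, except at 100 mg, where the two agree.

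**Step 4. Check the opposite misreading.** A reader who assumes that inhibitor is a slip for substrate, and changes that one word, would then halve venetoclax for a narrow-index substrate. Table 7 does not ask for that. Changing one word therefore does not repair the sentence; it has to be split.

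**The case against.** The strongest reply is that the correct rule is hard to miss. Table 7 sits in the same section, directly after the paragraph, and the paragraph ends by pointing to it. Section 8.13 names Table 7 before it names Section 8.8.4. Within the paragraph, the rifampin rationale and the resumption rule both refer to P-gp inhibitors without qualification, and the first instruction is to avoid these drugs altogether. This stands, and it is why the point is minor. It does not make the sentence correct.

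A second reply is that the 400 mg example names no drug. The P-gp inhibitors named in the protocol fall under separate CYP3A rules. Ketoconazole is a strong CYP3A inhibitor, so after ramp-up it requires a reduction of at least 75% (0.25 × 400 mg = 100 mg at most). Rifampin is a strong CYP3A inducer, contraindicated in ramp-up and to be avoided afterwards. This also stands. The example applies only to a P-gp inhibitor with no relevant CYP3A effect, and the documents name none. The gap for substrates is more concrete, because Section 8.8.4 itself lists digoxin, everolimus and sirolimus as P-gp substrates.

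A third reply is that adopting Table 7 leaves a mismatch over BCRP inhibitors: Section 8.10.1 includes them in its dose-adjustment requirement, but Table 7's reduction rule does not. That is true but separate. It neither excuses the sentence nor counts against correcting it.

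**Conclusion.** The concern holds. The Section 8.8.4 sentence gives the wrong trigger for both actions, and Table 7 has the intended rules. The size is a dose instruction only: 400 mg against at most 200 mg, or 200 mg against at most 100 mg, plus a missing timing rule for narrow-index substrates. This assumes a patient past ramp-up, an unavoidable P-gp inhibitor that is not narrow-index and falls under no CYP3A rule, and a site that follows the sentence without consulting Table 7. No effect on exposure or toxicity is estimated, because the only exposure figures in the documents come from a single dose of rifampin. No endpoint, analysis set or planned analysis is affected. The correction is desirable but not critical.

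**What to change.** Let Table 7 prevail. Delete the combined sentence in Section 8.8.4 and put Table 7's two rules in its place: "If a P-gp inhibitor must be used, reduce venetoclax dose by at least 50%, but not below 100 mg after the ramp-up phase", followed by "If a narrow therapeutic index P-gp substrate must be used, it should be taken at least 6 hours before venetoclax". The monitoring and resumption sentences that follow can stay, since they already refer to P-gp inhibitors without the qualifier. Table 7 and Sections 8.10.1 and 8.13 need no change for this correction.

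The cost is one sentence replaced by two. The visit schedule, data collection and analysis do not change.

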8.6 Dose Modifications of MOR00208

In a phase I study of MOR00208 in CLL, the MTD was not reached and the drug was generally well tolerated, IRRs of grade 1 or 2 being the most common toxicities. Treatment-related grade 3 or 4 AEs occurred in 5 out of 27 patients and included neutropenia, thrombocytopenia, increased AST, febrile neutropenia, and TLS. There was one CLL patient with dose-limiting toxicity (DLT) of grade 4 neutropenia lasting ≥ 7 days with febrile neutropenia

Dose reductions of MOR00208 are not allowed during the course of the study due to the relatively mild AE profiles of MOR00208.

In the case of clinically significant grade ≥ 3 toxicities that are not described in Table 8 & Table 9 and Sections 8.9 & 8.10:

- MOR00208 doses should be omitted until the toxicity grading diminishes in severity to grade ≤ 1 or returns to a baseline grade, provided the condition was pre-existing at baseline
- Missed doses of MOR00208 should not be made up for. If the patient misses a subsequent MOR00208 dose, the second missed dose should be administered immediately after the toxicity resolves.
- During monthly treatment with MOR00208, every missed dose should be administered immediately after the toxicity resolves.

If the Investigator considers a clinical finding and/or laboratory parameter change to represent natural fluctuation or progression of the underlying disease, then it will be at the Investigator's discretion (and depend on the assessment of the individual risk/benefit ratio) to determine whether the patient should be dosed. The decision and rationale behind the decision should be documented in the source data.

For MOR00208 dose modification instructions for specific toxicities, see Table 8 & Table 9 and Sections 8.9 & 8.10.

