8.7 Dose Modifications of Idelalisib

In the event of severe or life-threatening toxicities related to idelalisib, the drug must be withheld until the toxicity is resolved. If resuming idelalisib after interruption, reduce the dose to 100 mg twice daily. Re-escalation to 150 mg twice daily is allowed at the Investigator's discretion.

Recurrence of severe or life-threatening idelalisib-related toxicity upon rechallenge should result in permanent discontinuation of idelalisib.

For dose modification instructions for specific toxicities related to idelalisib, see Section 8.9 and Table 8.

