Management: In patients with Grade ≤ 3 anemia dosing of idelalisib and MOR00208 should be maintained as per protocol. Transfusion and growth factor support can be considered in accordance with institutional guidelines. In patients with **Grade 4** idelalisib and MOR00208 should be withheld until Grade 3 and hemoglobin should be monitored at least weekly. Thereafter, dosing may be maintained as per protocol.

Anaphylaxis

Background: Serious allergic reactions, including anaphylaxis, have been reported in patients on idelalisib.

Management: In patients who develop serious allergic reactions, idelalisib and MOR00208 administration must be discontinued permanently and appropriate supportive measures should be instituted.

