8.10.2 Management of Hematologic Toxicities

Background: Grade 3 or 4 neutropenia and febrile neutropenia occurred in 41% (98/240) and 5% of patients treated with venetoclax, respectively. Dosage adjustments of venetoclax due to adverse reactions occurred in 9.6% of patients. The most frequent adverse reactions leading to dose adjustments of venetoclax were neutropenia, febrile neutropenia, and thrombocytopenia. Most hematological toxicities AEs were first reported in the initial months of treatment of venetoclax, with highest incidence and prevalence of AEs in the first month and decreasing with time on study (Davids et al., 2016). Moreover, autoimmune hemolytic anemia (AIHA) and anemia were reported among the most frequent serious adverse reactions ($\geq 2\%$). The most frequent adverse reactions leading to drug discontinuation were thrombocytopenia and AIHA.

Serious infections including events of sepsis with fatal outcome have been reported in patients treated with venetoclax.

Treatment-emergent Grade 3 or 4 neutropenia occurred in 7% of MOR00208-treated patients in a phase I clinical trial in R/R CLL. There was one CLL patient treated with MOR00208 who experienced DLT of Grade 4 neutropenia lasting ≥ 7 days with febrile neutropenia in a phase I clinical trial of R/R CLL.

Management: Interrupt venetoclax and MOR00208 at 1st occurrence of Grade 3/4 neutropenia with infection or fever, or Grade 4 hematologic toxicities (except lymphopenia). Once the toxicity has resolved to Grade 1 or baseline level, venetoclax and MOR00208 therapy may be resumed at the same dose of venetoclax.

At 2nd and subsequent occurrences interrupt venetoclax and MOR00208. Consider transfusion and growth factor support as clinically indicated in accordance with institutional guidelines. Follow dose reduction guidelines in [Table 6](#) when resuming treatment with venetoclax after resolution. A larger dose reduction may occur at the discretion of the physician, but not below 100 mg daily dose after the ramp-up phase.

At 2nd and subsequent occurrences withhold MOR00208 and may resume as follows:

- Neutropenia: monitor ANC at least weekly until $ANC \geq 0.5 \times 10^9/L$ and/or neutropenic fever or infection is resolved
- Thrombocytopenia: monitor platelet count at least weekly until platelet count reach $\geq 25 \times 10^9/L$
- Anemia: monitor at least weekly until Grade 3

Thereafter, may resume as per protocol.

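### Table 8 labels the anemia row that maintains dosing as Grade ≥3, which takes in Grade 4, where the next row and Section 8.9.6 withhold both drugs (minor)

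*Protocol*

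**What the plan says.** Three places in the protocol set the Cohort A rule for anemia.

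- **Section 8.9, Table 8, Anemia, first row.** The label is Grade ≥3, with the bracket "Grade 3 defined as: Hemoglobin <8.0 g/dL; <4.9 mmol/L; <80 g/L; transfusion indicated". For each of the two drugs the instruction is: "Maintain dosing as per protocol. Consider transfusion and growth factor support in accordance with institutional guidelines".
- **Section 8.9, Table 8, Anemia, Grade 4 row.** For idelalisib: "Withhold idelalisib until Grade 3 and monitor at least weekly. Thereafter, maintain dosing as per protocol". The MOR00208 column says the same for that drug.
- **Section 8.9.6, Anemia.** For patients with Grade ≤3, "anemia dosing of idelalisib and MOR00208 should be maintained as per protocol". For Grade 4, "idelalisib and MOR00208 should be withheld until Grade 3 and hemoglobin should be monitored at least weekly".

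Two general rules also bear on the point. Section 8.7 says: "In the event of severe or life-threatening toxicities related to idelalisib, the drug must be withheld until the toxicity is resolved". Section 8.6 has a general hold for MOR00208 at clinically significant Grade 3 or higher toxicity, but limits it to "toxicities that are not described in Table 8 & Table 9 and Sections 8.9 & 8.10".

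Cohort B is governed by Table 9 and Section 8.10.2. At the first occurrence, both drugs are interrupted for "Grade 4 hematologic toxicities (except lymphopenia). Once the toxicity has resolved to Grade 1 or baseline level, venetoclax and MOR00208 therapy may be resumed". At later occurrences of anemia, MOR00208 is withheld until Grade 3.

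**The concern.** A site that looks up Grade 4 anemia in Table 8 finds it covered twice: by the Grade ≥3 row, which keeps both drugs going, and by the Grade 4 row, which stops both. A dose-modification table should give one action per grade, most of all for the grade it calls life-threatening.

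The general rules only partly repair this. Section 8.7 points to withholding, but covers idelalisib alone and only events related to it. The general MOR00208 hold in Section 8.6 excludes toxicities described in Table 8, and anemia is one of them. For MOR00208 the reader has to resolve the table internally or go to Section 8.9.6.

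Cohort A also has no hemoglobin floor at entry: in Section 7.2.1 the 8.0 g/dL minimum applies to Cohort B only. A Cohort A patient can therefore start treatment already in the range that Table 8 calls Grade 3. This gives no Grade 4 rate, but it shows that the anemia rows are not remote from the patients being treated.

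**Working it through.** No arithmetic applies to the rule itself, so the check sets the texts side by side.

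**Step 1: action by grade, Cohort A, same for both drugs.**

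| Source | Grade 3 | Grade 4 |
|---|---|---|
| Table 8, first anemia row, as labelled (≥3) | maintain | maintain |
| Table 8, Grade 4 anemia row | not covered | withhold until Grade 3 |
| Section 8.9.6 | maintain (≤3) | withhold until Grade 3 |

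The maintain row covers Grade 3 and above; the withhold row covers Grade 4. They overlap at Grade 4, with opposite actions.

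**Step 2: which text is wrong.** The Grade 4 row and Section 8.9.6 give the same action and the same release point. The first row's label is the only outlier. In Cohort B, Table 9 and Section 8.10.2 also interrupt MOR00208 at Grade 4 hematologic toxicity. No other anemia rule in the protocol continues dosing at Grade 4.

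**Step 3: is the overlap a convention of the table?** Row labels by grade number for the seven event types in Table 8 that are split this way:

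| Event type | Grade rows | Grade number under both maintain and withhold |
|---|---|---|
| Neutropenia | 2; 3; 4 or fever/infection | none |
| Thrombocytopenia | 2; 3; 4 | none |
| Anemia | ≥3; 4 | Grade 4 |
| Dermatological | ≤2; 3 or 4 | none |
| Gastrointestinal | all grades (work-up); 2; 3; 4 | none |
| Hepatic | 2; 3; 4 | none |
| Pulmonary | 1; 2; ≥3 | none |

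The count is 1 of 7 event types, in 2 of 2 drug columns. Neutropenia overlaps by condition (Grade 3 with fever or infection), not by grade number. The conditional holds for Grade 3 diarrhea (MOR00208) and Grade 1 pneumonitis (idelalisib) each sit within a single row. Three event types put an inequality on the grade number itself: anemia, dermatological and pulmonary. The other two fit their neighbouring rows without overlap.

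**Step 4: effect of the correction.** With the label changed to Grade ≤3, the maintain row covers Grades 1 to 3 and the withhold row covers Grade 4. The overlap is gone, and Table 8 matches Section 8.9.6.

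**The case against.** The strongest counter-argument is that nobody would be misled. The label's bracket defines Grade 3 only, Grade 4 has its own adjacent row with its own description, and Section 8.9.6 states the full rule clearly. Section 8.6 also closes by sending the reader to Tables 8 and 9 and Sections 8.9 and 8.10 for specific MOR00208 toxicities, so it does lead to Section 8.9.6, which names MOR00208. All of this is right, and it is why the point is minor. It does not make the label correct: a reader must recognise that the specific row overrides the general one, and the table should not require that.

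A second objection is that the whole point rests on one symbol in text read from a PDF by a program, and that single-character misreadings may occur elsewhere in that text. A misread sign cannot be fully excluded. It is unlikely, since both ≤ and ≥ appear in sensible places elsewhere in Table 8, and ≤ appears in Section 8.9.6. A glance at the signed protocol settles it.

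Third, the 1 of 7 count describes the table and does not measure harm. That is also correct. The count shows only that the overlap is not a house style; it says nothing about how often a patient would be misdosed.

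**Conclusion.** The inconsistency is real as the text stands. Table 8 tells Cohort A sites both to maintain and to withhold idelalisib and MOR00208 at Grade 4 anemia. The intended rule is to withhold, as the Grade 4 row and Section 8.9.6 both say.

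Its size is small: one label, one event type and one cohort, with the correct rule recoverable from the adjacent row. No endpoint, analysis or sample size is affected. The documents give no Grade 4 anemia rate for the combination, so no probability of misdosing can be derived. The conclusion assumes that the ≥ sign in the supplied text is the one printed in the protocol.

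**What to change.** In Section 8.9, Table 8, Anemia, change the first row's label from Grade ≥3 to Grade ≤3, as in Section 8.9.6. Leave the Grade 4 row unchanged. A plain Grade 3 label would also remove the overlap, but Grade ≤3 matches Section 8.9.6 exactly. Check the sign against the signed protocol before issuing the correction.

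The cost is one symbol in one row. Section 13.7.1 already provides an administrative route for typographical corrections and clarifications of confusing wording; the sponsor would need to confirm that this change qualifies. Nothing in the SAP needs to change.
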